11.4 Definitions

The NCI Working Group criteria (Hallek, 2008) will be used to assess response to therapy.

11.41 COMPLETE CLINICAL RESPONSE (CCR) requires all of the following at the Day 43 evaluation:

11.411 Absence of lymphadenopathy (e.g. lymph nodes >1.5 cm) by physical examination.

11.412 No hepatomegaly or splenomegaly by physical examination.

11.413 Absence of constitutional symptoms.

11.414 CBC demonstrating:

- Peripheral blood lymphocytes <4000/ μ L.
- Neutrophils >1500/ μ L
- Platelets >100,000/ μ L (untransfused).
- Hemoglobin >11.0 g/dL (untransfused).

Note: Patients who fulfill all criteria for a CCR but who have a persistent anemia, thrombocytopenia, or neutropenia related to drug toxicity rather than residual CLL will be classified as **CCR with incomplete marrow recovery (CCRi)** according to the international criteria (Hallek, 2008).

- 11.42 **PARTIAL RESPONSE (PR)**: PR requires the patient exhibits at least two of the features in Sections 11.421, 11.422, and 11.423 below (**if** abnormal prior to therapy) as well as **one or more** of the remaining features (Sections 11.424, 11.425, 11.426) at the day 43 evaluation. For patients with Rai stage 0 disease (e.g. no palpable nodes or organomegaly) and those with MBL a 50% reduction in lymphocytosis will be considered to represent a PR. In addition to the parameters listed below, the presence or absence of constitutional symptoms will be recorded.
- 11.421 $\geq 50\%$ decrease in peripheral blood lymphocyte count from the pretreatment baseline value.
- 11.422 $\geq 50\%$ reduction in the sum of the products of the maximal perpendicular diameters of the largest measured node or nodal masses in the right and left cervical, axillary, and inguinal lymph node regions on physical examination.
- 11.423 $\geq 50\%$ reduction in size of liver and/or spleen as measured by physical exam noting the maximal distance below the respective costal margins of palpable hepatosplenomegaly during rest.
- 11.424 Neutrophils $>1500/\text{ul}$ or 50% improvement over baseline.
- 11.425 Platelets $>100,000/\text{ul}$ or 50% increase over baseline.
- 11.426 Hemoglobin $>11.0 \text{ gm/dl}$ or 50% increase over baseline without transfusions.
- 11.43 **PROGRESSION (PD)**: Patients will be considered to have PD according to the NCI criteria²⁴ if they experience any of the following:
- 11.431 $\geq 50\%$ increase in the sum of the products of at least 2 lymph nodes (at least one node must be $\geq 2 \text{ cm}$) or the appearance of new palpable lymph nodes $>1.5 \text{ cm}$ **not due to a tumor flare**. Enlargements or the appearance of new nodes due to a tumor flare do NOT qualify as progression. If there is uncertainty as to whether lymph node enlargement at the Day 43 evaluation represents tumor flare, repeat examination 2-4 weeks after the protocol specified discontinuation of lenalidomide can be used to help make this determination.
- 11.432 $\geq 50\%$ increase in the size of the liver and/or spleen as determined by measurement below the respective costal margin on 2 consecutive determinations 2 weeks apart and with a minimum of a $\geq 2 \text{ cm}$ increase in size from baseline; or appearance of hepatomegaly or splenomegaly which was not previously present at baseline and **not due to a tumor**

flare. If there is uncertainty as to whether an increase in liver/spleen size at the Day 43 evaluation represents tumor flare, repeat examination 2-4 weeks after the protocol specified discontinuation of lenalidomide can be used to help make this determination.

- 11.433 Transformation to a more aggressive histology (e.g. Richter's transformation).

NOTE: If a patient develops DLBCL at any time, it will be considered progressive disease. If the patient develops any other hematological malignancy while on study, it will not be considered progressive disease.

- 11.434 $\geq 50\%$ increase in the absolute number of circulating lymphocytes NOT due to infection or tumor flare (taking as reference for progressive disease the smallest absolute lymphocyte count recorded since the treatment started).

- 11.435 Cytopenias due to lenalidomide toxicity will **not** be considered to represent disease progression. In the absence of progression as defined by 11.431, 11.432, 11.433, 11.434 above, the presence of a ≥ 2 g/dL decrease in HGB, or $\geq 50\%$ decrease in platelet count, or absolute neutrophil count will NOT be considered progression. Work-up of such decreases to exclude auto-immune hemolytic anemia, pure red cell aplasia, or idiopathic thrombocytopenic purpura (ITP) should be considered.

- 11.44 STABLE DISEASE (SD): Patients who do not meet criteria for CCR (or CCRi), PR, or PD will be classified as having "stable disease".

- 11.45 Not progressive disease (Not PD): The patient did not meet the criteria for progression per section 11.43 (MBL patients only).

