3.0 Patient Eligibility

3.1 Inclusion Criteria

- 3.11 Diagnosis of:
- CLL according to the NCI criteria (Hallek 2008)²⁴ or
 - SLL according to the WHO criteria (Harris, 1999)²⁵ or
 - MBL according to the consensus criteria (Marti 2006)²⁶

This includes **previous** documentation of:

- Biopsy-proven small lymphocytic lymphoma (Harris, 1999)
or
- Diagnosis of CLL²⁴ or MBL²⁶ as evidenced by all of the following:
 - ✓ Clonal B-cell population in the peripheral blood with immunophenotyping consistent with CLL defined as:
 - The population of lymphocytes share both B-cell antigens [CD19, CD20 (typically dim expression), or CD23] as well as CD5 in the absence of other pan-T-cell markers (CD3, CD2, etc.)
 - Clonality as evidenced by κ (kappa) or λ (lambda) light chain expression (typically dim immunoglobulin expression) or other genetic method (e.g. IGHV analysis)

NOTE: Splenomegaly, hepatomegaly, or lymphadenopathy are not required for the diagnosis of CLL

- ✓ Patients with a peripheral blood B-cell lymphocyte count of $<5 \times 10^9/L$ and no evidence of lymphadenopathy or organomegaly will be classified as MBL. Patients with a peripheral blood B-cell lymphocyte count of $<5 \times 10^9/L$ who have evidence of lymphadenopathy will be classified as SLL. Patients with a peripheral blood B-cell lymphocyte count $\geq 5 \times 10^9/L$ will be considered to have CLL.

- ✓ Before diagnosing MBL, CLL or SLL, mantle cell lymphoma must be excluded by demonstrating a negative FISH analysis for t(11;14)(IgH/CCND1) on peripheral blood or tissue biopsy or negative immunohistochemical stains for cyclin D1 on involved tissue biopsy.
- 3.12 CLL or SLL patients only (does not apply to MBL patients): Rai Stage 0-1 (both CLL and SLL patients can be staged using the Rai system).
- 3.13 Patients must not previously have received the Prevnar 13 pneumococcal vaccination. NOTE: Previous vaccination with Pneumovax (PCV23) is permitted but must have been at least 365 days prior to registration.
- 3.14 Patients must be previously untreated (see note) and **must NOT** have any of the following indications for chemotherapy:
- Evidence of progressive marrow failure as manifested by the development of or worsening anemia (≤ 11 g/dL) and/or thrombocytopenia ($\leq 100 \times 10^9/L$) not due to autoimmune disease
 - Symptomatic or progressive lymphadenopathy, splenomegaly or hepatomegaly.
 - One or more of the following disease-related symptoms:

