11.5 Summary Definition of objective response for patients with B-CLL

	CCR ¹	CCRi ²	PR ³	PD ⁴
PHYSICAL EXAM				
Nodes ⁵	None	None	≥50% ↓	≥50% ↑, new nodes
Liver/spleen ⁶	Not palpable	Not palpable	≥50% ↓	≥50% ↑, newly palpable
Symptoms	None	None	N/A	N/A
PERIPHERAL BLOOD				
ANC	>1500/μL	See footnote 2	>1500/μL	See footnote 4
Platelets	>100,000/μL	See footnote 2	>100,00/μL	See footnote 4
Hemoglobin	>11.0 g/dL without transfusion	See footnote 2	>11.0 g/dL	See footnote 4
Lymphocytes	<4000/μL	<4000/μL	≥50% ↓	≥50% ↑ to at least 5,000/μL
BONE MARROW	N/A	N/A	N/A	N/A

1. Clinical complete response (CCR) requires fulfillment of all physical exam and peripheral blood criteria as noted in the table above. No bone marrow biopsy is required to call a patient a CCR.
2. Patients who fulfill all criteria for a CCR but who have a persistent anemia, thrombocytopenia, or neutropenia related to drug toxicity rather than residual CLL will be classified as CCR with incomplete marrow recovery (CCRi).
3. Partial response (PR) requires fulfillment of at least two of the above-noted decrease in circulating lymphocytes, regression in adenopathy and regression in hepatosplenomegaly, and at least one other parameter listed above for a duration of >2 months after the completion of treatment. See Section 11.42.
4. Progression: Fulfilling the criteria as noted in section 11.43.
5. Measurement of lymphadenopathy will be determined on physical exam by adding the sum of the products of the maximal perpendicular diameters of measured lesion(s). For purposes of determining CCR all nodes on physical exam need to be ≤ 1.5 cm in maximal dimension or documented to be free of CLL by biopsy. NOTE: Information from CT scans regarding lymphadenopathy is not considered in the standard classification of response.
6. Measurement of hepatosplenomegaly will be determined by noting the maximal distance below the respective costal margins of palpable hepatosplenomegaly during rest (e.g., not during deep inspiration). NOTE: Information from CT scans regarding hepatosplenomegaly is not considered in the standard classification of response.

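### The lymphocyte criterion for progression has no minimum count in Section 11.434 but a 5,000/µL minimum in table 11.5, so low-count patients can be classified either way

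*Combined protocol and SAP*

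**What the plan says.** All references are to the combined protocol and SAP.

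- **Section 11.43** assigns PD to patients "if they experience any of the following", so one criterion is enough. Item 11.434 is a rise of at least 50%, described as an "increase in the absolute number of circulating lymphocytes NOT due to infection or tumor flare", and "taking as reference for progressive disease the smallest absolute lymphocyte count recorded since the treatment started". It gives no minimum count and asks for no confirmatory count.
- **Table 11.5**, PD column, lymphocyte row, gives the same 50% rise but adds "to at least 5,000"/µL. Its title is "Summary Definition of objective response for patients with B-CLL". Footnote 4 reads "Progression: Fulfilling the criteria as noted in section 11.43".
- **Section 11.45** defines the alternative to PD for MBL: "The patient did not meet the criteria for progression per section 11.43 (MBL patients only"). It does not mention the table.
- **Section 11.414** sets the lymphocyte limit for CCR at below 4,000/µL.
- **Section 16.321** groups CLL patients as responders (CCR, CCRi, PR) or non-responders (SD, PD), and MBL patients as PD or Not PD. It compares the arms by Fisher's exact test.

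**The concern.** The plan gives two definitions of one event, and the footnote that should link them points from the version with a floor to the version without one. A patient whose count goes from 2,000 to 3,000/µL has progressed under the text and has not under the table. Disease status is a secondary endpoint that is tested between arms, so its classification should not depend on which page the assessor consults.

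Two consequences follow if the text is applied. A patient can satisfy CCR and PD at the same visit, and no order of precedence is stated. In MBL, where the PD/Not PD split rests on Section 11.43 alone, a small absolute fluctuation at a low count can meet the criterion.

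**Working it through.** The plan states no figure on this point, so there is nothing to reproduce. The check compares the two rules and then sizes chance PD.

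**1. Where the rules disagree (CLL/SLL).** Let R be the reference count and D the Day 43 count.
- Text: PD if D ≥ 1.5 × R.
- Table: PD if D ≥ 1.5 × R and D ≥ 5,000/µL.
- They differ when 1.5 × R ≤ D < 5,000, which needs R < 5,000 / 1.5 = 3,333/µL.

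Under the table, the rise needed for PD is (5,000 / R − 1): 67% from 3,000, 100% from 2,500, 150% from 2,000 and 233% from 1,500/µL. From 3,334/µL upward both rules require 50%.

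**2. Overlap of CCR and PD.** CCR needs D < 4,000/µL. Under the text, PD by lymphocytes can occur at the same visit if R < 4,000 / 1.5 = 2,667/µL. Example: a Rai 0 patient with 8,000/µL before treatment, 2,000 on Day 15 and 3,000 on Day 43, with every other CCR item met. The Day 43 count is below 4,000 (CCR) and exactly 50% above the smallest count (PD under 11.434). With the table's floor the two calls cannot coincide on this criterion, because D cannot be both below 4,000 and at least 5,000.

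**3. MBL.** Section 3.11 defines this group by a B-cell count below 5 × 10⁹/L "and no evidence of lymphadenopathy or organomegaly will be classified as MBL". Section 11.45 sends these patients to 11.43 only, and the table's title names B-CLL. For MBL, therefore, the issue is a missing floor, not two rules in conflict.

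**4. Chance PD with no true change.** The documents give no within-person CV, so a range is assumed. Counts are taken as independent and lognormal with a stable mean, and s = √ln(1 + CV²).
- One reference count: P = 1 − Φ(ln 1.5 / (s√2)). At CV 20%, s = 0.198, so P = 1 − Φ(0.4055 / 0.280) = 7.4%.
- Lowest of two reference counts: by simulation.

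| Assumed CV | Day 15 only | Lower of baseline and Day 15 |
|---|---|---|
| 10% | 0.2% | 0.4% |
| 15% | 2.7% | 4.9% |
| 20% | 7.4% | 12.7% |
| 25% | 12.2% | 20.1% |

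These figures hold at any count level, so they do not measure the effect of the floor. That effect, at CV 20% with two reference counts, is:

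| Mean count (/µL) | Without floor | With 5,000/µL floor |
|---|---|---|
| 2,000 | 12.7% | about 0% |
| 3,000 | 12.7% | 0.4% |
| 4,000 | 12.7% | 6.5% |
| 5,000 | 12.7% | 11.9% |
| 6,000 | 12.7% | 12.7% |

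If 4,000/µL is read as the median instead of the mean, 7.1% remains in place of 6.5%.

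**The case against.** Several limits on the point are fair.

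- **Few patients may fall in the zone of conflict.** CLL requires a B-cell count of at least 5 × 10⁹/L, so a CLL patient at that level must fall by more than a third before R drops below 3,333/µL. The MBL limit is on B cells, not total lymphocytes, so some MBL patients will also have R above 3,333/µL. The documents do not show how many patients would have low counts. This stands.
- **Noise alone does not move the CLL comparison.** SD and PD are both non-responders in 16.321. Only a CLL/SLL patient who would otherwise be CCR, CCRi or PR can change group. In MBL, PD against Not PD can move directly. This stands.
- **The reference count is ambiguous.** Baseline is drawn before registration (Section 4.0) and treatment cannot begin before registration (6.17). Read literally, Day 15 is the only scheduled reference before Day 43, which gives the lower column of figures. In Arm B the only treatment is the Day 15 vaccine (7.1), so even Day 15 is arguable there. This stands and is a reason to define the reference.

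A reader might infer that the version without a floor governs. Footnote 4 points that way, but the table cell states the floor, so the documents do not settle it.

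A reader might also infer that the missing floor biases Arm A toward PD, because a count that dips on lenalidomide and returns to its start has risen 50% from a one-third fall. The documents do not support this as an effect of the floor. A path of 9,000, 6,000, 9,000/µL is PD under both rules. Lenalidomide runs to Day 42 and status is judged at the Day 43 visit, so off-drug recovery would mainly need an interruption or early stop. Tumor flare is already excluded. Extra weekly counts after grade 3 or higher neutropenia (8.2) could lower the recorded minimum in Arm A, but nothing shows how often.

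**Conclusion.** The conflict is plain on the page and should be corrected. For CLL/SLL the two rules give different calls when the reference is below 3,333/µL and the Day 43 count is below 5,000/µL. Under the text alone, CCR and PD can both be met when the reference is below 2,667/µL, and this result needs no assumption about variability. For MBL no floor applies as written, and at low counts ordinary variation could produce PD.

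The size of the chance effect rests on the assumed CV: negligible at 10%, and at 20–25% between 7% and 20% depending on the reference. It would be wrong to read that range as the gain from adding the floor. The floor removes nearly all of it at 2,000–3,000/µL, about half at 4,000/µL and almost none from 5,000/µL.

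The effect is confined to the disease-status secondary endpoint. The primary OPA response is untouched.

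**What to change.** Before any patient's disease status is classified:

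1. Reconcile 11.434, the table 11.5 PD cell and footnote 4 into one lymphocyte criterion. Carrying the table's floor into 11.434 is the simplest way, and it also removes the CCR/PD overlap.
2. State in 11.45 whether that criterion applies to MBL. If the floor goes into 11.434 it will reach MBL through the existing cross-reference, so this should be a deliberate choice.
3. State whether the pre-treatment baseline count is part of the reference, preferably by naming the visits so that both arms use the same ones.

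The cost is a phrase in 11.434 and one sentence each for MBL and the reference count. No visit, sample or test is added. The floor will not remove chance PD, or PD from a dip and return, at higher counts.

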11.5 Summary Definition of objective response for patients with B-CLL

	CCR ¹	CCRi ²	PR ³	PD ⁴
PHYSICAL EXAM				
Nodes ⁵	None	None	≥50% ↓	≥50% ↑, new nodes
Liver/spleen ⁶	Not palpable	Not palpable	≥50% ↓	≥50% ↑, newly palpable
Symptoms	None	None	N/A	N/A
PERIPHERAL BLOOD				
ANC	>1500/μL	See footnote 2	>1500/μL	See footnote 4
Platelets	>100,000/μL	See footnote 2	>100,00/μL	See footnote 4
Hemoglobin	>11.0 g/dL without transfusion	See footnote 2	>11.0 g/dL	See footnote 4
Lymphocytes	<4000/μL	<4000/μL	≥50% ↓	≥50% ↑ to at least 5,000/μL
BONE MARROW	N/A	N/A	N/A	N/A

1. Clinical complete response (CCR) requires fulfillment of all physical exam and peripheral blood criteria as noted in the table above. No bone marrow biopsy is required to call a patient a CCR.
2. Patients who fulfill all criteria for a CCR but who have a persistent anemia, thrombocytopenia, or neutropenia related to drug toxicity rather than residual CLL will be classified as CCR with incomplete marrow recovery (CCRi).
3. Partial response (PR) requires fulfillment of at least two of the above-noted decrease in circulating lymphocytes, regression in adenopathy and regression in hepatosplenomegaly, and at least one other parameter listed above for a duration of >2 months after the completion of treatment. See Section 11.42.
4. Progression: Fulfilling the criteria as noted in section 11.43.
5. Measurement of lymphadenopathy will be determined on physical exam by adding the sum of the products of the maximal perpendicular diameters of measured lesion(s). For purposes of determining CCR all nodes on physical exam need to be ≤ 1.5 cm in maximal dimension or documented to be free of CLL by biopsy. NOTE: Information from CT scans regarding lymphadenopathy is not considered in the standard classification of response.
6. Measurement of hepatosplenomegaly will be determined by noting the maximal distance below the respective costal margins of palpable hepatosplenomegaly during rest (e.g., not during deep inspiration). NOTE: Information from CT scans regarding hepatosplenomegaly is not considered in the standard classification of response.

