4.0 Test Schedule

Tests & Procedures	Active Monitoring Phase				
	Days Prior to Registration	Day 15 (+/- 3 days)	Day 28 (+/- 7 days)	Day 43 (+/- 4 days)	Observation: 28 days after end of first cycle (Day 72 +/- 10 days)
	≤14 days				
Medical history	X				
Adverse event assessment	X	X		X	X
Physical exam, including PS, weight and vital signs	X			X	X
Height	X				
Register in the REVLIMID REMS® program (Arm A only)	X ⁸				
Counseling for the REVLIMID REMS® program (Arm A only)			X		
Tumor measurement by physical exam	X ¹			X ¹	
Peripheral blood immunophenotyping by flow cytometry	X ²				
CBC with differential and reticulocytes	X	X		X	X
Serum pregnancy test	X ³	X ³	X ³	X ³	
Chemistry group (SGOT [AST], SGPT [ALT], total bilirubin, serum creatinine, calcium, alkaline phosphatase, uric acid, LDH, potassium)	X	X		X	
Glucose	X				
Direct bilirubin	X ⁷				
CD38	X ²				
ZAP-70	X ²				
IGHV	X ⁴				
CD49d	X ⁴				
Serum protein electrophoresis	X			X	
Beta-2-microglobulin	X				
Peripheral blood CLL FISH panel	X ⁶				
Serum quantitative immunoglobulins (IgG, IgA, IgM)	X			X	
Coombs test (monospecific direct coombs IgG and C3)	X				
EKG	X				
Quantitative T & B cells, peripheral blood	X			X	

Prevna 13 pneumococcal vaccination		X			
Research blood specimens (see Section 14.0)	X ^{5,R}	X ^{5,R}		X ^{5,R}	

1. Physical exam should measure the spleen and liver noting the maximal distance below the respective costal margins and should record the bidimensional diameter of the largest palpable node in each area of involvement including the following sites: left neck (sub-mandibular, cervical, supra-clavicular), right neck (sub-mandibular, cervical, supra-clavicular), left axillary, right axillary, left groin (inguinal, femoral) and right groin (inguinal, femoral).
 2. May be waived for patients who have previously had full flow immunophenotyping consistent with CLL performed at Mayo Clinic. Similarly, if the patient has previously had CD38 and/or ZAP-70 testing performed at Mayo Clinic, repeat assay is elective after discussing with the study chair.
 3. For women of childbearing potential only. Must follow pregnancy testing requirements as outlined in the Revlimid REMS® program material.
 4. If patient has previously had done clinically at Mayo Clinic, this does not need to be repeated.
 5. Blood specimens will be collected and submitted at baseline, Day 15 and Day 43. Kits are required.

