11.21 CLL/SLL: Disease status will be classified as one of the following using the criteria below which are based on the IWCLL criteria without the bone marrow biopsy results²⁴:

- progressive disease
- stable disease
- partial response
- clinical complete response (or clinical complete response with incomplete marrow recovery)

11.22 MBL: Disease status will be classified as one of the following criteria based on the IWCLL criteria for progressive disease:

- progressive disease
- not progressive disease

11.3 For the purposes of this study, patient's disease status will be evaluated at the time of the day 43 evaluation. Although the patient will be periodically seen Days 1 - 42, response evaluations will not occur on those dates.

NOTE: Information from CT scans is not considered in the standard classification of response.

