13.0 Treatment/Follow-up Decision at Evaluation of Patient

NOTE: As of Addendum 4, Event monitoring will no longer be required

- 13.1 After completion of the Day 43 response to vaccine evaluation, patients will discontinue treatment and enter one cycle of OBSERVATION (28 days after end of first cycle +/- 10 days) and then enter EVENT MONITORING.
- 13.2 If Lenalidomide is discontinued due to patient refusal or noncompliance, unacceptable toxicity, or intercurrent illness that makes treatment assessment difficult and the patient received the Prevnar 13 vaccine, they will receive their Day 43 response to vaccine evaluation at which point they will then enter one cycle of OBSERVATION (28 days after end of first cycle +/- 10 days) and then enter EVENT MONITORING.
- 13.3 If a patient on Arm A does not receive the Prevnar 13 vaccine, they will discontinue treatment and go directly to event monitoring per Section 18.0 of the protocol. If a patient on Arm B does not receive the Prevnar 13 vaccine, they will be deemed a cancel and will be removed from the study per Section 13.6 of the protocol.
- 13.4 A patient is deemed *ineligible* if after registration, it is determined that at the time of registration, the patient did not satisfy each and every eligibility criteria for study entry.
 - If the patient received treatment, the patient will go directly to event monitoring. All data up until the point of confirmation of ineligibility must be submitted. Event monitoring will be required per Section 18.0 of the protocol.
 - If the patient never received treatment, on-study material and the End of Active Treatment/Cancel Notification Form must be submitted. No further data submission is necessary.

Note: Due to the nature of the disease, if the patient is diagnosed with DLBCL within the first cycle of treatment, it will be assumed that the DLBCL was present at registration. The patient will be deemed ineligible per Sec 3.29c.
- 13.5 A patient is deemed a *major violation*, if protocol requirements regarding Lenalidomide treatment during Days 1-42 are severely violated such that evaluability for primary end point is questionable. All data up until the point of confirmation of a major violation

must be submitted. The patient will go directly to the event-monitoring phase of the study. Event monitoring will be required per Section 18.0 of the protocol.

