16.321 Disease status by physical exam and complete blood counts will be evaluated in each patient. For CLL, each patient will be classified as CCR, CCRi, PR, SD, or PD per Section 11.2 at the time of the 6 week assessment of immune response. The distribution of disease status will be evaluated in each arm and will be summarized descriptively. Patients will be classified as responders (CCR, CCRi, PR) vs. non-responders (SD, PD). For MBL, patients will be classified as Not PD vs. PD. Differences in disease status response will be compared between the two arms using Fisher's exact test.

16.322 Time to treatment for progressive CLL will be defined as the time from the date of registration to the date of initiation of treatment for progressive CLL. The distribution of time to treatment will be estimated in each arm using the method of Kaplan-Meier. Time to treatment will be compared between the two arms using log-rank statistics.

16.323 Adverse Events: All eligible patients that have initiated treatment will be considered evaluable for assessing adverse event rate(s). Platelets and hemoglobin will be graded according to the Grading Scale for Hematologic Adverse Events in CLL Studies in Appendix IV. The maximum grade for each type of adverse event will be recorded for each patient, and frequency tables will be reviewed for each arm to determine

patterns. Additionally, the relationship of the adverse event(s) to the study treatment will be taken into consideration.

16.33 Correlative Analyses:

16.331 Pre-vaccination (day 15) and day 28 post-vaccination OPA GMTs for each serotype (4, 9V, 23F) will be reported in the vaccine and vaccine + lenalidomide groups. The fold-change in OPA GMT from baseline to 28 days post-vaccination will be evaluated for each serotype, where two-sample t-tests will be used to compare GMTs between the vaccine and vaccine + lenalidomide groups.

16.332 Pre-vaccination (day 15) and day 28 post-vaccination *Streptococcus pneumoniae* serotype specific IgG GMTs for each serotype (1, 3, 4, 5, 6B, 7F, 9V, 14, 18C, 19F, 19A, and 23) will be reported in the vaccine and vaccine + lenalidomide groups. The fold-change in quantitative IgG GMT from pre-vaccine (day 15) to 28 days post-vaccination will be evaluated for each serotype, where two-sample t-tests will be used to compare GMTs between the vaccine and vaccine + lenalidomide groups.

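### Footnote 3 of Table 11.5 adds a two-month duration to partial response that conflicts with assignment at Day 43 and cannot be met, on the current visit schedule, by Arm A patients who complete lenalidomide

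*Combined protocol and SAP*

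**What the plan says.** **When status is assigned.** Section 11.3 states that "patient's disease status will be evaluated at the time of the day 43 evaluation". Section 11.42 defines PR by features present at the Day 43 evaluation and sets no duration. Section 16.321 classifies CLL patients at the 6-week assessment, groups complete clinical response (CCR), CCR with incomplete marrow recovery (CCRi) and PR as responders against stable disease (SD) and progression (PD), and compares the arms by Fisher's exact test. Section 11.44 makes SD the residual class.

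**What the table adds.** Footnote 3 of Table 11.5 repeats the PR criteria, adds "for a duration of >2 months after the completion of treatment", and then refers to 11.42. The table's footnotes for CCR and CCRi carry no duration.

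**What follow-up exists.** The last column of the test schedule in Section 4.0 is "Observation: 28 days after end of first cycle (Day 72 +/- 10 days". Section 13.1 says that after the Day 43 evaluation "patients will discontinue treatment and enter one cycle of OBSERVATION (28 days after end of first cycle +/- 10 days". The note at the head of Section 13.0 says: "As of Addendum 4, Event monitoring will no longer be required". Section 18.1 repeats that note.

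**MBL.** Section 11.42 says that for "those with MBL a 50% reduction in lymphocytosis will be considered to represent a PR", whereas Section 16.321 says "For MBL, patients will be classified as Not PD vs. PD". Sections 11.22 and 11.45 agree with 16.321.

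**The concern.** Two definitions of PR stand in the current text. One can be applied at the Day 43 visit. The other needs an observation more than two months after treatment, which the schedule does not appear to provide. PR counts as a response and SD does not, so the choice of definition can move a patient across the line that the Fisher's exact test compares. The definition also depends on when treatment ended. The two arms have different last treatments (lenalidomide to Day 42 in Arm A, one vaccine dose on Day 15 in Arm B), so a duration clause may act differently in each.

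**Working it through.** The plan gives no expected rate or power for disease status, so there is no design figure to reproduce for this endpoint. The check is a day count.

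**Inputs**
- Planned last lenalidomide dose: Day 42 (Section 7.1, Appendix V).
- Treatment stop as worded in Section 13.1: after the Day 43 evaluation.
- Arm B vaccine: Day 15, visit window +/- 3 days, so Days 12 to 18 (Sections 4.0, 7.1).
- Observation visit: Day 72 +/- 10, so Days 62 to 82 (Section 4.0).
- Two months: not defined in days in the plan. Assumed to be 60 days; two calendar months span 59 to 62.

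**The plan's own visit day.** 28 days after the end of the cycle is 42 + 28 = Day 70, or 43 + 28 = Day 71. Section 4.0 prints Day 72. The difference lies well inside the window and does not matter here.

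**Formula.** Days observable after treatment = day of Observation visit − day treatment ended.

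| Treatment taken to end | Earliest visit | Nominal visit | Latest visit |
|---|---|---|---|
| Day 42 (last lenalidomide dose) | 62 − 42 = 20 | 72 − 42 = 30 | 82 − 42 = 40 |
| Day 43 (Section 13.1) | 62 − 43 = 19 | 72 − 43 = 29 | 82 − 43 = 39 |
| Day 15 (Arm B vaccine) | 62 − 15 = 47 | 72 − 15 = 57 | 82 − 15 = 67 |

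Using both visit windows, the Arm B row runs from 62 − 18 = 44 to 82 − 12 = 70 days.

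**Shortfall for Arm A completers.** The first day more than 60 days after Day 42 is 42 + 61 = Day 103. The latest visit is Day 82, so the schedule ends 103 − 82 = 21 days short. Counting from Day 43 gives Day 104 and 22 days short. Any length of two months from 59 to 62 days exceeds 40, so the conclusion does not depend on the 60-day assumption. The optional repeat examination for suspected tumor flare (Sections 11.431 and 11.432) is 2 to 4 weeks after lenalidomide stops, at most 28 days, and does not close the gap.

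**Arm B if completion is the Day 15 vaccine.** The first qualifying day is 15 + 61 = Day 76, which lies inside the Day 62 to 82 window. At the nominal Day 72 visit the patient does not qualify (57 days); late in the window the patient does.

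**Arm A early stoppers.** A patient who stopped lenalidomide by 82 − 61 = Day 21 could pass 60 days by Day 82. Section 13.2 keeps such a patient on the Day 43 and Observation visits if vaccinated.

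**What is measured at Observation.** Section 4.0 schedules physical examination and blood counts there, but formal tumor measurement only at baseline and Day 43. Section 18.1 nevertheless lists a Measurement form at Observation. Even a visit late enough to qualify may therefore lack the nodal measurements.

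**Resulting classification.** Take an Arm A completer who meets every PR feature of 11.42 on Day 43 and does not meet CCR or CCRi. Under 11.42 the class is PR: responder. Under footnote 3 the duration cannot be shown, so PR fails, 11.44 gives SD, and 16.321 counts a non-responder.

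**The case against.** The best defence is that the text largely settles the timing itself. Table 11.5 is only a summary. Its footnote sends the reader to 11.42, and goal 2.21 with Sections 11.2, 11.3, 11.42 and 16.321 all point to Day 43 or 6 weeks. An analyst would probably follow those. That stands as a reason to rate the point as minor, but it does not remove the conflict: 11.42 contains no duration, so referring to it does not cancel one that the footnote adds.

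The footnote's grammar also allows the duration to attach only to the additional blood-count parameter. That parameter is no more observable beyond two months than the rest.

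A reader might infer more than the documents support:
- **That no patient in either arm can be PR, so the PR rate is 0%.** Arm B may be counted from Day 15, and early Arm A stoppers could also qualify. Section 13.1 does have all patients discontinue after Day 43, but Arm B has no agent left to discontinue then. Patients followed before Addendum 4 may also have had event monitoring: Section 18.1 shows a form every 6 months for up to 2 years after registration, with documentation of response or progression. The documents do not date Addendum 4, so later information on such patients cannot be ruled out.
- **That the responder comparison loses its main category.** No expected PR, CCR or CCRi rate is given, the trial does not set out to treat the CLL (Section 11.2), and CCR and CCRi remain responders on any reading.
- **That the MBL wording alters a result.** Sections 11.22, 11.45 and 16.321 all use only PD or not PD, and Table 11.5 is headed for B-CLL. The MBL sentence feeds no analysed category.

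**Conclusion.** The conflict is real and small. For Arm A patients who take lenalidomide to Day 42 and have no event monitoring, the footnote cannot be met: at most 40 days are observable against more than two months required. Any of them who is PR under 11.42 would be scored SD and a non-responder under the footnote. If Arm B completion is the Day 15 vaccine, some Arm B patients could meet it (44 to 70 days observable), so the footnote would make PR harder to attain in Arm A completers than in Arm B for reasons unrelated to disease. How many patients this would move cannot be estimated, because the plan gives no PR rate.

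This rests on the current schedule and on a literal reading of the footnote. It reaches one secondary endpoint, disease status under goal 2.21. The primary vaccine-response endpoint, the 26 patients per arm and the stated 80% power do not use it. The MBL wording is editorial.

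**What to change.** Delete the duration clause from footnote 3 of Table 11.5, so that PR is assigned at Day 43 as in 11.3, 11.42 and 16.321. State in 16.321 that PR is an unconfirmed Day 43 status. Make the change before any patient's disease status is classified for analysis, so that the choice of definition cannot follow the data.

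The change removes one phrase and adds a label; it needs no new visit, sample or patient. The price is that PR no longer carries any claim of durability. That is all a single Day 43 assessment can support.

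As a separate tidy-up, reconcile the mention of MBL in the PR sentence of 11.42 with 11.22, 11.45 and 16.321, most simply by removing it. No analysed result changes.
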